- b) Subjects who prematurely discontinue study drug will require an immediate EOT assessment (either on the day of study drug discontinuation or as soon as possible following study drug discontinuation). Subjects that discontinue study drug early will continue in the study and be assessed with the off-treatment procedures at the subsequent visit(s) per the Schedule of Activities, starting at the next scheduled visit from when study drug was permanently discontinued up to the final Week 12 visit. These off-treatment procedures will include assessment and collection of SAEs, specific AEs of interest (ie, major adverse cardiac events, acute pancreatitis, and possible cases of thyroid neoplasm), vital signs (including body weight), and concomitant medications.
- c) The SAE follow-up visit will be conducted for all subjects approximately 5 weeks after the last dose of study drug to collect serious adverse events since the last visit unless the subject has died, has been lost to follow-up, or has withdrawn consent. Blood samples will also be collected for PK and immunogenicity (ie, anti-drug antibody) measurement. Subjects who prematurely discontinue study drug for any reason prior to Week 12 and have not withdrawn consent, will continue (off-treatment) in the study following the EOT visit and undergo the off-treatment procedures based on the predefined study visit schedule.
- d) Informed Consent must be signed at the screening visit before any study procedures are performed.
- e) Record any medications taken from up to 30 days before screening (and up to 6 months before screening for AHA) until the first dose of treatment phase study drug on Day 1 (baseline) as prestudy therapy in the corresponding eCRF. Concomitant therapy includes all medications taken since the first dose of treatment phase study drug on Day 1.
- f) Subjects will be asked to perform a self-injection of open-label JNJ-64565111-matching placebo (Week -2) or their randomly-assigned study drug (Day 1) at the study site in the presence of the study-site staff. After Day 1, injections may be performed by the subject at home.
- g) A survey will be given to English-speaking subjects to assess subject satisfaction with the experience of self-administering JNJ-64565111 or matching placebo.

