4.3. Justification for Dose

Dose Selection and Dose Interval of JNJ-64565111

The $t_{1/2}$ of 6 to 8 days allows for a weekly dosing frequency for JNJ-64565111. While in earlier Phase 1 studies, JNJ-64565111 was administered using weight-based doses, fixed doses of JNJ-64565111 were tested in Study 64565111EDI1002. As such, the dosing regimen is more practical and is likely to be associated with greater adherence. Fixed weekly doses of 5 and 10 mg of JNJ-64565111 in the Phase 1 Study 64565111EDI1002 showed similar exposures compared with doses of 1.0 and 2.0 nmol/kg/week observed in the previous Phase 1 MAD study (HM-OXM-101; see Section 2.2, Background). Moreover, fixed dosing resulted in overall similar variability in exposure compared with body weight-based dosing for equivalent doses of 5 and 10 mg of JNJ-64565111. In 4-week studies in overweight and obese subjects with T2DM, doses of JNJ-64565111 in this dose range resulted in approximately 2% to 4% reduction in body weight. As this duration of treatment is too short to observe the full weight-loss potential of any pharmacological intervention, this study is being conducted with the doses specified for 12 weeks of treatment. Twelve weeks is generally sufficient to assess weight loss and any significant safety issues in a Phase 2 study. The upper end of the dose range was selected because drug exposures are highly variable beyond doses of 10 mg weekly ([Study 64565111EDI1002](#)). Moreover, doses above 10 mg, while leading to greater weight loss, also appeared to be less tolerated as indicated by a dose-dependent increase in the incidence in GI AEs as well as increase in mean pulse rate. The 7.4 and 10 mg doses are expected to produce clinically meaningful weight reduction and are therefore included in the study. The 5-mg dose was included to add a third anchor point, which is needed to evaluate a dose-response relationship as suggested by the dose-response guidance International Conference on Harmonisation (ICH) E4 (which states: *Several dose levels are needed, at least 2 in addition to placebo, but in general, study of more than the minimum number of doses is desirable*).

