9.2. Sample Size Determination

A total of 188 subjects will be randomly assigned in this study with 47 subjects per group allocated to each of the 4 treatment groups. Sample size was determined based on assessing the primary hypothesis that treatment with JNJ-64565111 at 1 or more dose levels for 12 weeks leads to greater percentage reduction in body weight compared with placebo.

Assuming a common SD of 4% with respect to percent change in body weight at Week 12 and a 2-sided type I error rate of 0.05, it is estimated that a sample size of 47 randomly assigned subjects per group will have approximately 90% power to detect a treatment difference of 2.7%.

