9.4.2. Safety Analyses

The evaluation of safety will be based on the incidence of adverse events and hypoglycemia episodes, and changes in clinical laboratory test results and vital sign results (blood pressure, pulse rate). The safety analyses will be based on the safety analysis set including all data, regardless of the initiation of glycemic rescue therapy (ie, including data after initiation of rescue therapy). Additional analysis of hypoglycemia will be performed based on the data prior the initiation of glycemic rescue therapy only. Summaries of adverse events, clinical laboratory test results, and vital sign results will be provided by treatment group. There will be no imputation of missing values for clinical safety laboratory test results, and vital sign measurements.

Adverse Events

The verbatim terms used in the eCRF by investigators to identify adverse events will be coded using the Medical Dictionary for Regulatory Activities (MedDRA). Treatment-emergent adverse events are adverse events with onset during the treatment phase or that are a consequence of a pre-existing condition that has worsened since baseline. All reported adverse events will be included in the analysis. For each adverse event, the percentage of subjects who experience at least 1 occurrence of the given event will be summarized by treatment group. In addition, comparisons between treatment groups will be provided if appropriate.

Summaries, listings, datasets, or subject narratives may be provided, as appropriate, for those subjects who die, who discontinue study drug due to an adverse event, or who experience a severe or a serious adverse event.

For each adverse event, the percentage of subjects who experience at least 1 occurrence of the given event will be summarized by treatment group. The percentage of subjects with specific treatment-emergent adverse events (TEAEs) will be summarized by severity and relationship to study drug, as classified by the investigator, by treatment group. The dose-response relationship of dose levels on TEAE will be assessed, assuming that the incidence rates of TEAE will be monotonic with respect to dose levels. A listing for non-TEAEs will be provided.

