Hypoglycemic events will be classified as severe, documented symptomatic, probable symptomatic and asymptomatic. The primary hypoglycemic analysis of interest will be all documented hypoglycemic events regardless of the presence of symptoms (ie, documented symptomatic and asymptomatic hypoglycemia) plus all severe hypoglycemic events. For each type of hypoglycemia, the percentage of subjects with at least one event will be summarized by treatment group. The differences in percentage (JNJ-64565111 versus placebo) and their 2-sided 95% confidence intervals will be estimated.

Hypoglycemic events are collected on a separate eCRF and also collected on the Adverse Event eCRF (for all such events considered as adverse events by the investigator). The primary analysis of hypoglycemia will be based upon data from the hypoglycemia eCRF (and not from the adverse event database). No reconciliation of hypoglycemia data from the Adverse Event eCRF and the hypoglycemic eCRF will be performed (except to assure that all adverse events of hypoglycemia are also recorded on the hypoglycemia eCRF).

Further analyses, to be described in the SAP for this study which will be finalized before the subject is randomized, will be conducted on the prespecified adverse events for which additional information is collected from the investigators (refer to Section 8.2, Safety Assessments), and on other adverse events.

Clinical Laboratory Tests

Laboratory data will be summarized by type of laboratory test. Normal reference ranges will be provided. Criteria for markedly abnormal laboratory values will be prespecified in the SAP. The percentage of subjects with markedly abnormal results will be summarized for each laboratory

analyte. Descriptive statistics will be reported for each laboratory analyte at baseline and at each scheduled time point and for change from baseline.

Resting Vital Signs (Pulse, Blood Pressure)

Descriptive statistics of pulse rate and sitting blood pressure (systolic and diastolic) values and changes from baseline will be summarized at each scheduled time point. The percentage of subjects with values beyond clinically important limits will be summarized.

Physical Examination

Physical examination findings will not be summarized except when reported as an adverse event.

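### Hypoglycemia is compared only as a crude percentage of subjects with an event, with no allowance for time observed, and the documents disagree on what is collected after early drug stop

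*Protocol*

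**What the plan says.** **Measure.** Protocol 9.4.2 states: "For each type of hypoglycemia, the percentage of subjects with at least one event will be summarized by treatment group". It adds a difference in percentages from placebo with a 95% CI. The primary hypoglycemia set is documented events, symptomatic or not, plus severe events. It is taken from the hypoglycemia eCRF rather than the adverse event database. SAP 6 has no hypoglycemia subsection and adds no person-time or recurrent-event measure.

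**Rescue.** The main safety analysis keeps data after rescue. In addition, Protocol 9.4.2 says: "Additional analysis of hypoglycemia will be performed based on the data prior the initiation of glycemic rescue therapy only". SAP 6 repeats this. Neither gives a time at risk for it.

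**Collection after early drug stop.** The passages point two ways.
- In the Schedule of Activities (Protocol 1.3), the row for recording SMBG and hypoglycemic episodes ends at Week 12/EOT. Early stoppers have an immediate EOT assessment. Footnote b then says: "These off-treatment procedures will include assessment and collection of SAEs, specific AEs of interest". The events of interest named there are MACE, pancreatitis and thyroid neoplasm, and the list goes on to vital signs and concomitant medications. Protocol 4.1 and 7.1 give the same list. Neither SMBG nor hypoglycemia is on it.
- Footnote y monitors adverse events to 5 weeks after the last dose. Protocol 8.3.1 reports serious and non-serious events up to the last study procedure. SAP 6.1 counts treatment-emergent events to last dose plus 35 days. Protocol 9.4.2 requires adverse events of hypoglycemia to appear on the hypoglycemia eCRF as well.

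**Exposure.** SAP 4.4 already summarises treatment duration by arm, overall and before rescue, but does not link it to hypoglycemia.

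**The concern.** A percentage with at least one event gives a subject observed for 3 weeks the same denominator weight as one observed for 12. If one arm has more early stops, it has had less time to record events, and its percentage falls for that reason alone. The pre-rescue analysis has the same feature for the arm with more rescue.

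The events most exposed are asymptomatic low readings and episodes not judged to be adverse events. They reach the eCRF through the diary, and they are part of the primary hypoglycemia set.

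Unequal observation is plausible but not documented. Protocol 7.1 contains mandatory stops tied to possible drug effects (severe vomiting, pulse rate, sodium). Protocol 2.3 says some subjects may have glucose raised by the drug, which bears on rescue.

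Protocol 4.2 names hypoglycemia as an example of a safety issue to be assessed in this population. The main risk is that a real excess on active drug is diluted. Repeat episodes are also recorded on the hypoglycemia eCRF but not analysed.

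**Working it through.** **1. The plan's own figures.** None concerns hypoglycemia. The only stated power is for body weight: "approximately 90% power to detect a treatment difference of 2.7" percent, with SD 4% and 47 per arm (Protocol 9.2). Check: 2.7 / (4 × √(2/47)) = 2.7 / 0.825 = 3.27, and Φ(3.27 − 1.96) = 0.905 (0.899 by noncentral t). It reproduces. Only the 47 per arm is used below.

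**2. Assumed inputs.** The documents give no hypoglycemia, stop or rescue rates. Assume a constant hazard, equal in both arms, with 12-week risk R, so λ = −ln(1 − R)/12 per week (0.0186 for R = 20%, 0.0297 for R = 30%). A share s of the active arm stops, with stop time t uniform from 0 to T weeks. Placebo has no stops. A stopper is observed for f = min(12, t + c) weeks, with c = 0 if capture ends at stop and c = 5 if every event is captured for 5 more weeks.

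Crude % = (1 − s)R + s·m, where m is the mean of 1 − exp(−λf). The true difference is zero.

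| R | s, T | m, c = 0 | Crude (error) | m, c = 5 | Crude (error) |
|---|---|---|---|---|---|
| 20% | 10%, 12 wk | 10.37 | 19.0 (−1.0) | 16.83 | 19.7 (−0.3) |
| 20% | 20%, 12 wk | 10.37 | 18.1 (−1.9) | 16.83 | 19.4 (−0.6) |
| 20% | 30%, 6 wk | 5.38 | 15.6 (−4.4) | 13.78 | 18.1 (−1.9) |
| 30% | 30%, 6 wk | 8.41 | 23.5 (−6.5) | 21.06 | 27.3 (−2.7) |

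**3. Stops in both arms.** Let 5% of placebo and 30% of active stop at Week 4, with R = 20%. A stopper's risk is 1 − 0.8^(4/12) = 7.17% (c = 0) or 1 − 0.8^(9/12) = 15.41% (c = 5).
- c = 0: active 0.7 × 20 + 0.3 × 7.17 = 16.15; placebo 0.95 × 20 + 0.05 × 7.17 = 19.36; difference −3.2 points.
- c = 5: 18.62 − 19.77 = −1.15 points.

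With a true hazard ratio of 1.5, the active 12-week risk is 1 − 0.8^1.5 = 28.45%, a true excess of 8.45 points. It shows as 3.7 points (c = 0) or 6.8 points (c = 5).

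**4. Against sampling error.** At 20% in both arms the 95% half-width is 1.96 × √(2 × 0.20 × 0.80 / 47) = 16.2 points. At 30% against 23.5% it is 17.9 points. Every error above is smaller.

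**5. What a rate does.** Under a constant hazard, expected first events equal λ times expected time at risk. First events divided by time at risk therefore return the same λ in both arms, whatever the stop times.

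**6. Rescue.** Suppose 20% of an arm are rescued uniformly over 12 weeks and have a 12-week risk of 5%, against 20% in the rest.
- True risk: 0.2 × 5 + 0.8 × 20 = 17.0%.
- Crude pre-rescue percentage: 0.2 × 2.52 + 0.8 × 20 = 16.5%, where 2.52% is the mean risk before a uniform rescue time.
- Kaplan-Meier censored at rescue: 18.4%, because rescued subjects are given the hazard of the rest.

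Here censoring errs by +1.4 points and the crude figure by −0.5.

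**The case against.** **Collection does not plainly end at drug stop.** A reader of the off-treatment list might infer that it does. The documents do not support that as fact: adverse event reporting stays open, and hypoglycemia judged an adverse event must go on the hypoglycemia eCRF. This stands, and it is why two sets of figures are shown. It does not remove the point, because episodes not judged adverse events have no scheduled route after an early EOT.

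**Collection does not end at rescue.** Rescued subjects stay on study drug and in the study (Protocol 4.1), and the main analysis uses their data. Only the additional analysis excludes it. This stands.

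**The direction is not established.** A reader might infer that active drug will look safer than it is. Protocol 4.3 does say "less tolerated as indicated by a dose-dependent increase in the incidence in GI AEs", but of doses above 10 mg, and none is tested here. A mandatory stop for glucose still high on rescue could fall on placebo. Phase 1 glucose results are mixed. The bias is conditional on which arm is observed for less time.

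**The percentage is a legitimate description.** SAP 6 plans no hypothesis tests on safety, and nothing commits the plan to a 12-week risk with everyone on drug. This stands as a reason to keep the percentages.

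**It is partly covered.** SAP 4.2 and 4.4 report stop reasons and duration by arm, and SAP 6.1 allows time-to-event assessment of adverse events flagged by its screen. These help interpretation. But the screen is optional, works on adverse events seen in at least four subjects in an arm, and does not cover the hypoglycemia eCRF as such.

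**Conclusion.** The point holds in a limited form. The only planned hypoglycemia comparison ignores time observed and repeat episodes, the pre-rescue analysis has no stated time at risk, and the passages on collection after early stop conflict.

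If stops differ by arm, the arm observed for less time is understated: by 0.3 to 2.7 points with full capture for 5 more weeks, and by 1.0 to 6.5 points with none after stop. The pre-rescue analysis would similarly understate the arm with more rescue, but its size depends on how the hazard in rescued subjects compares with the rest.

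These figures rest on assumed risks of 20% or 30%, assumed stopping of 10% to 30% in one arm and none in the other, and a constant hazard. They are below the sampling error of a single comparison, so they would not overturn a conclusion on their own. They are systematic, though, and would persist if data were pooled. It would go too far to say that the planned interval is invalid or that a bias in favour of active drug is shown.

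**What to change.** 1. Reconcile the Schedule of Activities and its footnote b, Protocol 4.1 and 7.1 with footnote y, Protocol 8.3.1 and SAP 6.1, so that it is clear whether hypoglycemia, including episodes not judged adverse events, is collected after early drug stop, and until when.
2. Keep the crude percentages. Add to SAP 6 an on-treatment rate per subject-year by arm, for first events and for all episodes, with a difference or ratio from placebo and 95% CI. Do this for the primary hypoglycemia set and for the pre-rescue analysis. The all-episode interval should allow for clustering of episodes within a subject.
3. Count events and time over the same window, using the overall and pre-rescue durations in SAP 4.4. That duration (last dose − first dose + 8 days) runs through 7 days after the last dose. Events should be counted to the same day, and both capped at EOT if the reconciled rule ends capture there. For first events, time stops at the event.
4. A Kaplan-Meier cumulative incidence may be shown as supportive only, with a statement that censoring at drug stop or rescue may be informative. The pre-rescue rate carries the same caution if read as a 12-week risk for all subjects.

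The cost is a document clarification, SAP wording and about two tables. Sample size and visits do not change, and data already planned for collection suffice. The rates will be imprecise if events are few, and they assume a roughly constant on-treatment rate.

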An increase in ketones is a normal physiologic response to fasting, prolonged exercise, and certain dietary weight-loss regimens (eg, low-carbohydrate, high-fat diets) in which fatty acids are transformed in the liver into the ketones, aceto-acetate, and β -hydroxybutyrate. Physiologically, these ketones are used by the brain and muscles, including the heart, as an alternative fuel source when glucose is not readily available (Laffel 1999). The production of free fatty acids and their conversion to ketone bodies is stimulated by glucagon and inhibited by insulin. In the presence of near-normal or normal insulin function, the rate of hepatic ketone formation is balanced by the rate of the body's ketones utilization and, to a certain degree, ketones loss into the urine. Although ketones can increase in the blood and urine under physiological conditions in subjects with and without diabetes and is termed "ketosis," under certain circumstances, ketones can accumulate to high levels and lead to an acidic state, termed "ketoacidosis," which is associated with significant illness and metabolic decompensation, requiring emergent medical attention. While ketoacidosis is known to occur in patients with type 1 diabetes (ie, diabetic ketoacidosis [DKA]), patients with T2DM can on very rare occasion develop ketoacidosis, especially in the absence of inadequate carbohydrate intake and insulin deficiency (either absolute or relative due to increased insulin resistance observed in acute illness). A 2- to 3-fold increase in the serum levels of the ketone, β -hydroxybutyrate (generally <1.0 mmol/L), relative to placebo was seen in the Phase 1 Studies 64565111EDI1001 and 64565111EDI1002 in which 50 subjects with T2DM (on either diet/exercise alone or on metformin monotherapy) were treated for 4 weeks with JNJ-64565111 which would be expected given the weight loss observed and the dual agonism of JNJ-64565111 at the GLP-1 and glucagon receptors. Importantly, in these 2 studies conducted in subjects with T2DM, no AEs of ketoacidosis or metabolic acidosis were reported. Therefore, subjects receiving JNJ-64565111 may develop ketosis due to reduced food intake/weight loss, but it is unlikely, although theoretically possible, that they could develop DKA under certain conditions. Subjects with signs and symptoms of DKA should have appropriate laboratory evaluations (eg, blood pH, serum β -hydroxybutyrate, anion gap) performed. Subjects who develop biochemically confirmed DKA will be permanently discontinued from study drug.

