The randomized study population consists of men and women, ages 18 to 70 years at screening, inclusive, with severe obesity (BMI ≥ 35 to ≤ 50 kg/m²) and T2DM (ie, HbA_{1c} of $\geq 6.5\%$ to $\leq 9.5\%$ at screening) treated with either diet/exercise alone or with single or dual oral AHA regimen. In this study, the definition of "severe" obesity, which is commonly used within the surgical community to refer to subjects who are eligible for bariatric surgery, is inclusive of the WHO definition of Obese Class II (35-39 kg/m²) and III (≥ 40 kg/m²) (WHO 2017). Consistent with Health Authority guidance, this study is being conducted in obese subjects with T2DM to understand the magnitude of weight loss and to assess any unique safety issues (eg, hypoglycemia) in this population. Given the potential contribution of weight loss on HbA_{1c}-lowering, the study will provide experience in severely obese subjects across a broad spectrum of different diabetes treatment regimens.

Choice of Efficacy Measures

The primary efficacy endpoint will be a comparison of percentage change in body weight between the JNJ-64565111-treated and placebo-treated groups. This is an accepted endpoint for clinical trials of weight management products (FDA 2009). Secondary and exploratory endpoints are also consistent with the current FDA and EMA guidelines for the development of weight-management drugs and will provide further information on the magnitude and proportion of subjects experiencing weight loss along with any potential impact on other weight related comorbidities (ie, glycemic control, vital signs, lipids), and PROs.

Rationale for Use of Placebo Control

A placebo control will be used to establish the frequency and magnitude of changes in clinical endpoints that may occur in the absence of active treatment, improving the precision of the assessments of both efficacy and safety. A study without a placebo arm cannot properly determine the weight-reducing efficacy of a weight management product, given the impact of co-interventions (eg, diet and exercise counseling). Similarly, given background occurrence of AEs in this population in which comorbidities are common, without a placebo treatment group, it is not possible to precisely define the safety and tolerability profile of a new weight management product.

Choice of Patient-Reported Outcome Measures

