5.1. Inclusion Criteria

Each potential subject must satisfy all of the following criteria to be enrolled in the study:

1. Male or female (according to their reproductive organs and functions assigned by chromosomal complement)
2. 18 (or the legal age of consent in the jurisdiction in which the study is taking place) to 70 years of age, inclusive
3. BMI ≥ 35 to ≤ 50 kg/m² at screening
4. Stable weight (ie, change of $\leq 5\%$ within 12 weeks before screening based on medical or subject reported history)
5. HbA_{1c} of $\geq 6.5\%$ and $\leq 9.5\%$ at screening as determined by the central laboratory and meets one of the inclusion criteria below:
 - On diet and exercise alone ≥ 12 weeks prior to screening
 - On stable dose of single oral AHA or dual-combination oral AHAs for ≥ 12 weeks prior to screening (AHAs allowed at screening include: metformin, sulphonylureas, DPP-4 inhibitors, SGLT-2 inhibitors, and TZDs)

6. Subjects are, in the investigator's opinion, well-motivated, capable, and willing to:
 - perform fasting SMBG testing at least 2 times per week
 - learn how to self-inject treatment, as required for this study
7. On Day 1, subjects must have 100% compliance with the open-label placebo run-in medication based on unused prefilled safety injector(s), used empty study drug carton(s), and/or injections recorded in study drug diary during the pretreatment phase.
8. Willing and able to adhere to the prohibitions and restrictions specified in this protocol
9. Must sign an informed consent form (ICF) indicating that he or she understands the purpose of, and procedures required for, the study and is willing to participate in the study.
10. Women must be either:
 - postmenopausal, defined as:
 - >45 years of age with amenorrhea for at least 18 months, or
 - >45 years of age with amenorrhea for at least 6 months and <18 months and a serum follicle-stimulating hormone (FSH) level >40 mIU/mL (>40 IU/L), or
 - permanently sterilized (eg, bilateral tubal occlusion [which includes tubal ligation procedures as consistent with local regulations], hysterectomy, bilateral salpingectomy, bilateral oophorectomy); or otherwise be incapable of pregnancy, or

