6.3. Measures to Minimize Bias: Randomization and Blinding

Randomization and Blinding Procedures

On Day 1, subjects will be randomly assigned to 1 of 4 treatment groups based on a computer-generated randomization schedule prepared before the study by or under the supervision of the sponsor. The randomization will use randomly permuted blocks.

At baseline (Day 1), the treatment code, which is linked to the randomization schedule, will be assigned after logging on to the IWRS designated by the sponsor. The requestor must use his or her own user identification and personal identification number when contacting the IWRS, and will then give the relevant subject details to uniquely identify the subject. Based on this information, the IWRS will assign a unique treatment code, which will dictate the treatment assignment and matching study drug kit for the subject. As subjects are randomly assigned to treatment, the IWRS will assign a study drug kit to be dispensed at that visit. New study drug kits will be assigned each time the IWRS is accessed for dispensing additional study drug.

Blinding

The investigator will not be provided with randomization codes. The codes will be maintained within the IWRS, which has the functionality to allow the investigator to break the blind for an individual subject.

Data that may potentially unblind the study drug assignment (ie, study drug serum concentrations, anti-JNJ-64565111 antibodies, study drug preparation/accountability data, study drug allocation, FPG, HbA_{1c}, serum β -hydroxybutyrate, and urine ketones) will be handled with special care to ensure that the integrity of the blind is maintained and the potential for bias is minimized. This can include making special provisions, such as segregating the data in question from view by the investigators, clinical team, or others as appropriate until the time of database lock and unblinding.

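### Hypoglycemia is compared with placebo only as a crude difference in percentages; stratifying by baseline sulphonylurea use would add a little precision and show the result by regimen.

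*Protocol*

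**What the plan says.** Inclusion criterion 5 (Protocol 5.1) admits subjects on diet and exercise alone or on one or two oral agents: "AHAs allowed at screening include: metformin, sulphonylureas, DPP-4 inhibitors, SGLT-2 inhibitors, and TZDs". Protocol 6.1 requires that regimen to stay unchanged through the study. Protocol 6.3 describes allocation as follows: "The randomization will use randomly permuted blocks". Neither that section nor SAP 1.5 names a stratification factor.

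For each type of hypoglycemia, Protocol 9.4.2 summarises the percentage of subjects with at least one event by arm and then states: "The differences in percentage (JNJ-64565111 versus placebo) and their 2-sided 95% confidence intervals will be estimated". The primary hypoglycemia analysis counts all documented events, with or without symptoms, plus all severe events. It is repeated on data before glycemic rescue (Protocol 9.4.2, SAP 6). The SAP adds no model, stratum or subgroup for hypoglycemia. The subgroups in SAP 2.3 are sex, age, race, BMI, HbA1c and HOMA-IR, and SAP 5.2.3 applies them to the primary efficacy endpoint only.

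Protocol 4.2 explains the choice of population partly by safety issues particular to T2DM, with hypoglycemia as the example. It adds that "the study will provide experience in severely obese subjects across a broad spectrum of different diabetes treatment regimens".

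**The concern.** Suppose hypoglycemia risk depends on whether a subject takes a sulphonylurea. Background use is then a prognostic baseline variable that is already recorded but used neither in allocation nor in the estimate. With 47 per arm, chance differences in use between a dose arm and placebo will be common. Such a difference moves the crude estimate in a known direction, and part of the scatter in that estimate could be removed.

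A reader who wants to know whether the drug raises hypoglycemia in sulphonylurea users, or only in others, will find no table that answers it. What is at stake is the sharpness and usefulness of one descriptive safety comparison. The validity of the trial is not in question.

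**Working it through.** **The plan's own figure.** The only sample-size statement concerns body weight. Its inputs (Protocol 9.2) are "Assuming a common SD of 4% with respect to percent change in body weight at Week 12", a "2-sided type I error rate of 0.05" and 47 per group, which "will have approximately 90% power to detect a treatment difference of 2.7" percentage points. The standard error is 4 × √(2/47) = 0.825. Then 2.7/0.825 = 3.27, and Φ(3.27 − 1.96) = 0.905 (0.899 with the noncentral t). The figure reproduces. No precision is stated for hypoglycemia, so that has to be worked out.

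**Assumptions.** The documents give neither the share of sulphonylurea users nor the event risks, and they do not say that this class changes hypoglycemia risk. I assume a share p of 20-40%, a risk r1 of 20-40% in users and a risk r0 of 3-5% in others. Risks are taken as equal across arms, with n = 47 per arm.

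**How often the arms differ by chance.** The SD of the difference in share is √(2p(1−p)/47), which is 8.3, 9.5 and 10.1 points at p = 20%, 30% and 40%. The chance of a gap of 5 or more users (10.6 points), in either direction, is:

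| Share of users | One given dose vs placebo | At least one of three doses |
|---|---|---|
| 10% | 12% | 28% |
| 20% | 25% | 51% |
| 30% | 31% | 61% |
| 40% | 34% | 66% |

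**What such a gap does.** Shift = (5/47) × (r1 − r0). With 20% against 3% this is 0.106 × 0.17 = 1.8 points. With 40% against 5% it is 0.106 × 0.35 = 3.7 points.

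**Crude interval and gain from stratifying.** Let m = p·r1 + (1−p)·r0 be the overall risk. The crude half-width is 1.96 × √(2m(1−m)/47). With use accounted for, m(1−m) is replaced by the within-stratum variance w = p·r1(1−r1) + (1−p)·r0(1−r0). The share of variance removed is 1 − w/[m(1−m)].

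| p | r1 vs r0 | m | Crude half-width | Variance removed | Half-width after | 5-user shift |
|---|---|---|---|---|---|---|
| 20% | 20% vs 3% | 6.4% | 9.9 | 7.7% | 9.5 | 1.8 |
| 20% | 40% vs 5% | 12.0% | 13.1 | 18.6% | 11.9 | 3.7 |
| 40% | 20% vs 3% | 9.8% | 12.0 | 7.8% | 11.5 | 1.8 |
| 40% | 40% vs 5% | 19.0% | 15.9 | 19.1% | 14.3 | 3.7 |
| 20% | 15% vs 5% (weaker) | 7.0% | 10.3 | 2.5% | 10.2 | 1.1 |
| 40% | 30% vs 10% (weaker) | 18.0% | 15.5 | 6.5% | 15.0 | 2.1 |

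Half-widths and shifts are in percentage points. Simulating the Mantel-Haenszel risk difference itself gives a variance reduction of 7-19% over the main range and 2-6% for the weaker contrasts. In the main range the half-width falls by 0.4 points (9.9 to 9.5) to 1.6 points (15.9 to 14.3). Both estimators averaged zero in the simulations, as they should with no drug effect.

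**The case against.** The strongest reply is that nothing is wrong with the planned comparison. Randomisation makes the crude difference unbiased, and its 95% interval already allows for chance imbalance in background drugs. SAP 6 rules out hypothesis tests on safety, so no decision rule is affected. The shift lies well inside the interval, and the small arms limit the answer more than the lack of adjustment does. All of this stands. A reader might infer from unstratified allocation that the hypoglycemia result is confounded; the documents do not support that.

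A reader might also infer that background agents are ignored. They are not. Antihyperglycemic history is recorded for up to 6 months before screening (Protocol 1.3, footnote e). SAP 4.6 tabulates prior and concomitant medications by arm and ATC term, so an imbalance would be visible. What that table does not do is link the agent to the outcome.

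A third tempting inference is that serum beta-hydroxybutyrate and SGLT-2 inhibitors raise an equal problem. The protocol does note that the Phase 1 subjects behind its ketone data were "on either diet/exercise alone or on metformin monotherapy", and Protocol 2.3 discusses ketoacidosis. But ketones are not an objective or endpoint, and Protocol 8.2.4 measures the analyte as a marker of target engagement. Change from baseline on a stable regimen already removes much of any constant background effect. The criterion above 2.0 mmol/L in SAP Attachment 2 would be too sparse to split. Assuming 10-30% SGLT-2 use and risks of 1% in non-users against 5-10% in users, about 0.7-1.7 cases per arm are expected. The chance that any arm reaches the 4 cases needed for an interval (SAP 6.2) is 2-33%.

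Finally, the Protocol 4.2 sentence on regimens opens with the effect of weight loss on HbA1c and promises experience, not safety results by regimen. It supports a descriptive table but does not oblige the sponsor to produce one.

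**Conclusion.** The point holds as a modest improvement. The protocol singles out hypoglycemia, yet the planned comparison does not use a recorded baseline variable that may predict it, and no output shows it by regimen. The crude estimate is unbiased and its interval valid. The cost is a slightly wider interval (about 0.4-1.6 points on half-widths of about 10-16) and a possible conditional shift of 1.8-3.7 points for a 5-user gap.

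These sizes rest on assumed use and risks and on the assumption that risk differs by sulphonylurea use. With weaker contrasts the variance gain is only 2-6%, and with no contrast there is neither shift nor gain. The primary efficacy analysis and its power are unaffected. The documents do not support extending the point to bias in the comparison or to a second key safety question on ketones.

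**What to change.** Before unblinding, add to SAP 6, for the primary hypoglycemia analysis (documented plus severe events), a Mantel-Haenszel risk difference for each dose against placebo with a 95% CI, stratified by baseline sulphonylurea use (yes/no). Report it alongside the crude difference. Tabulate incidence by arm and sulphonylurea use, and label the by-stratum results descriptive. Keep sparse categories such as severe events descriptive only.

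A descriptive summary of serum beta-hydroxybutyrate by baseline SGLT-2 use is optional. Adding agent class to SAP Table 4.1.1 would largely duplicate SAP 4.6 and is not needed.

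The cost is a paragraph of SAP text and a few tables from data already collected. Design, conduct and sample size do not change. The downside is small strata: at 20-40% use there are about 9-19 users per arm (0.20 × 47 to 0.40 × 47), so estimates within strata will be imprecise.
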